## 2. Study Objectives

The primary purpose of this program is to enable patients, currently receiving sorafenib (Nexavar) in a Bayer/Onyx sponsored clinical trial, to continue sorafenib treatment after their respective study has met its primary endpoint and/or has reached the end as defined in the original protocol.

Patients will be able to continue treatment until (i) the treating physician feels the patient is no longer benefiting from the treatment or (ii) the treatment becomes commercially available and reimbursed for the respective indication as applicable in the country in which the patient lives and the patient can obtain suitable amounts of drug for treatment through standard mechanisms of commercial availability (i.e., there should be no interruption in the patient's treatment schedule when switching to commercially available product) or (iii) the patient can join a Post-Trial-Access Program, another study or can receive sorafenib through any other mechanism (e.g. local access program) in accordance with local legal and compliance rules, with no cost to the patient with respect to sorafenib.

An additional objective is the assessment of the safety of Nexavar or Nexavar combination treatment.

## 3. Study Design

This is an open label program that will enable patients receiving sorafenib (Nexavar) in a completed Bayer/Onyx sponsored clinical trial to continue treatment. A completed study is one that has passed the official statistical and regulatory endpoints and/or has reached its end, as outlined in that protocol. The patients in this open-label program will continue receiving sorafenib treatment at the same dose and schedule as in their original Clinical Trial.

Patients will continue receiving treatment, as long as the treating physician feels the patient is continuing to benefit from treatment or until treatment becomes commercially available and reimbursed for the respective indication in the country in which the patient lives or until being switched to any other form of drug supply with no interruption in the patient's treatment schedule. The patient may also continue treatment until he/she withdraws consent, is non-compliant, is lost to follow up, or if an unacceptable toxicity occurs.

Further details can be found in the protocol.

## 4. General Statistical Considerations

### 4.1 General Principles

The statistical evaluation will be performed by using the software package SAS release 9.2 or higher (SAS Institute Inc., Cary, NC, USA).

The creation of tables will follow the Bayer Therapeutic Area Standards (TAS) for Oncology and the Global Medical Standards (GMS).

All variables will be analyzed by descriptive statistical methods. The number of data available and missing data, mean, standard deviation, minimum, quartiles, median, and maximum will be calculated for metric data. Frequency tables will be generated for categorical data.

The analysis is limited to the data coming from this study.

Tables will be created by treatment group (sorafenib monotherapy, sorafenib+erlotinib). For the disposition data, baseline data and ECOG data, the total will also be displayed. Safety data (adverse events, laboratory data) will not be combined across the treatment groups. Since there is only one patient with sorafenib+erlotinib treatment, safety data from the patient with sorafenib+erlotinib will only be listed.

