10.2.1 Overview of Changes

Modification: Inclusion and Exclusion Criteria

An inclusion criterion was added to allow subjects who received combination treatment with sorafenib (Nexavar) and TACE (transarterial chemoembolization) in their originating study to be eligible for this extension study. The exclusion criterion regarding concurrent anti-cancer chemotherapy was, therefore, modified to clarify that the exclusion did not apply to subjects being treated with sorafenib in combination with TACE.

This change was made to allow subjects from the SPACE study to continue to receive sorafenib under this extension protocol. The SPACE study, a randomized, double-blind study of sorafenib vs placebo in patients with hepatic cellular carcinoma who are receiving TACE treatment, will be closed in the near future. Subjects from this study who are receiving sorafenib and continue to benefit from the therapy may now, under this amendment protocol be enrolled in the STEP program may continue to receive TACE along with sorafenib.

In addition, this single criterion covering concurrent anti-cancer chemotherapy, concurrent immunotherapy, and concurrent hormonal therapy was split into three distinct bullets. This change was made clarity and does not represent a change to study conduct.

The protocol sections affected by these changes are [Section 4.2.1](#), Inclusion Criteria, and [Section 4.2.2](#), Exclusion Criteria.

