10.4.1 Overview of Changes

Modification 1 Change of responsibility for the Study Manager and Medical Expert.

Contact names for the Study Manager and Medical Expert were updated on the title page of the protocol. A line was also added for the signature of the Global Clinical Lead.

The protocol section affected by this change is the title page.

Modification 2 Removal of all references to erlotinib.

All references to erlotinib were removed since none of the subjects that transferred into this study were assigned to erlotinib+sorafenib in study 12917 (SEARCH). Where entire sections were removed, this also changed the section numbering in subsequent sections and tables.

The protocol sections affected by this change are Section 4.1 Study design and Plan, Section 4.2.1 Inclusion Criteria, Section 4.2.2 Exclusion Criteria, Section 4.5.1 Treatments to be Administered, Section 4.5.2.2 Sorafenib and erlotinib combination therapy, Section 4.5.2.2.1 Anti-rash and Anti-diarrhea Therapies, Section 4.5.2.2.2 Dose Modification for Hand-Foot Skin Reaction, Section 4.5.2.2.3 Dose Modification for Keratitis, Section 4.5.2.2.4 Dose Modification for Interstitial Lung Disease, Section 4.5.3.2 Erlotinib, Section 4.5.5 Selection of Doses in the Study, Section 4.5.6 Selection and Timing of Dose for Each Subject and Section 4.5.8 Prior and Concomitant Therapy.

Modification 3 Clarification regarding the supply of capecitabine for subjects from Study 12444 changing from clinical supply by the sponsor to commercial supply.

The protocol current language suggest that for those subjects who will be transferred from the RESILIENCE study (12444) and taking a combination of capecitabine and sorafenib, both sorafenib and capecitabine will be provided by the sponsor. However, capecitabine is

commercially approved for breast cancer and readily available in many countries including generic sources, the study team proposes to modify the protocol to reflect that capecitabine will NOT be provided by the sponsor but should be sourced from commercial sources for those subjects who are on combination treatment. Only sorafenib will be provided by the sponsor.

The protocol sections affected by this change are Section 4.1 Study design and Plan, Section 4.5.1 and Treatments to be Administered and Section 4.5.3.3 Capecitabine.

Modification 4 Removal of references to placebo in association with sorafenib administration in Study 12444 (RESILIENCE).

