In Study 12444 (RESILIENCE), subjects received either capecitabine and sorafenib or capecitabine and placebo. In this protocol, the text as written can be misinterpreted to indicate that subjects from Study 12444 received both sorafenib and placebo and none of the subjects received sorafenib and placebo in Study 12444. This modification removes the word placebo when referring to subjects in Study 12444 who received sorafenib.

The protocol sections affected by this change are Section 4.5.2.2 Sorafenib and capecitabine combination, Section 4.5.2.2.2 Dose modification for hematologic toxicities, Section 4.5.2.2.3 Dose modification for non-hematologic toxicities, Section 4.5.2.2.4 Dose modification and management of sorafenib-specific toxicities and Section 4.5.2.2.6 Dose modification for other non-hematologic toxicities (excluding fatigue, dermatologic toxicities, gastrointestinal toxicities, hypertension and toxicities attributable to capecitabine).

Modification 5 Addition of TACE to the permissible anticancer chemotherapies in Section 4.5.8 Prior and Concomitant Therapy and addition of guidance on Sorafenib dose modification in combination with TACE in Section 4.5.2.3.

One of the changes implemented during Amendment 2 (16 Mar 2011) was to modify the exclusion criteria to allow patients who were receiving TACE and sorafenib in a Bayer

sponsored study to participate in the STEP study. This is reflected in protocol Section 4.2.2 (Exclusion criteria) and in Section 10.2.2 that describes the changes and rationale for the amendment. However, Section 4.5.8 (Prior and Concomitant Therapy) was not modified to allow the concomitant use of TACE and sorafenib and is not in line with the intent of Amendment 2 and the related text in Section 4.2.2.

The lack of changing Section 4.5.8 to be in line with the other sections of the protocol was an unintentional oversight. The study team issued an administrative letter on 11 Dec 2013 to clarify that since the implementation of Amendment 2, concomitant TACE and sorafenib is permissible as *per the protocol* (Section 4.2.2 and 10.2.2). This discrepancy in Section 4.5.8 is now being corrected in this amendment to reflect that TACE is permissible.

Meanwhile, the guidance on Sorafenib dose modification in combination with TACE is added as the Section 4.5.2.3.

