11.1 Study Flow Chart

Activity ^{zzzz}	Visit 1	Minimum Every 8 weeks (±7 days) ^{aaaaa}	End of Treatment
Demography ^{a, b}	X		
Pregnancy Test	X		
Vital signs	X	X	X
ECOG performance ^a	X	X	X
Survival status (dead or alive, date of death or date of last contact, as applicable) ^{bbbb}		X	X ^d
Adverse events ^a			
All treatment related	X	X	X
All Grade 3 or higher regardless of attribution	X	X	X
All serious adverse events	X	X	X
Laboratory evaluations ^a			
Hematology (Hgb, RBC, WBC, platelets, differential)	X	X	X
CBC (ALT, AST, amylase, lipase)	X	X	X
PT-INR ^c			
Dispense/return sorafenib (and capecitabine if applicable) ^{cccc} ^{dddd} ^a	X	X	X
Reason for termination of treatment ^a			X
Concomitant medications	X	X	X

a Record these data in the CRF and source documents.

b Includes originating study number, patient number and date of first sorafenib dose in originating study.

c For anticoagulated patients only

d The long term follow up period is until 30 days after last dose of study drug.^{eeee} ^{ffff}

^{zzzz}: The text row regarding date of death was deleted in Amendment 3. See Section 10.3, Modification 6.

^{aaaaa} The visit window has been modified by Amendment 7. See Section 10.5.3, Modification 3.

^{bbbb}: The text row concerning survival was added in Amendment 3. See Section 10.3, Modification 1.

^{cccc} Reference to erlotinib removed since none of the subjects that transferred into this study were assigned to erlotinib from study 12917. See Section 10.4, Modification 2.

^{dddd}: Participation of subjects from the SEARCH trial (Study 12917) or the RESILIENCE trial (Study 12444) was added under Amendment 3. See Section 10.3, Modification 5

^{eeee}: The table footnote regarding assessment of survival was added in Amendment 3. See Section 10.3, Modification 1.

^{ffff} The table footnote was revised to change the FU period to until 30 days after last dose of study drug in Amendment 7. See Section 10.5.5, Modification 5.

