**Table 1–1: Patient numbers of study 12311 by feeder trial**

Feeder trial number	Number of Patients, n (%)
100375	3 (1.5)
100554	24 (11.7)
100557	1 (0.5)
10874	1 (0.5)
10916	1 (0.5)
11213	18 (8.7)
11538	3 (1.5)
11546	1 (0.5)
11559	1 (0.5)
11718	1 (0.5)
11721	6 (2.9)
11848	12 (5.8)
11849	1 (0.5)
11868	5 (2.4)
11941	65 (31.6)
11961	7 (3.4)
11988	3 (1.5)
12007	4 (1.9)
12347	2 (1)
12782	4 (1.9)
12913	7 (3.4)
12917	7 (3.4)
12918	4 (1.9)
13266	5 (2.4)
14295	7 (3.4)
14898	13 (6.3)
Total	206 (100)

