#### **4.5 Data Rules**

Baseline value for laboratory measurements and ECOG performance status are the last non-missing values documented before or on the day of first study medication administration in the STEP study.

In this study, adverse events (AEs) ongoing from previous study could also be documented in addition to newly occurring AEs. Since the STEP data are not combined with data from the feeder trials, the start and stop dates of sorafenib treatment in the feeder trial are not available and it cannot be derived if the ongoing AEs are treatment-emergent or not. The ongoing AEs will therefore be analyzed separately and not termed 'treatment-emergent'. AEs in STEP are considered as treatment-emergent, if they start or worsen from enrolment date in STEP and up to 30 days after the last sorafenib dose. New non-treatment emergent AEs are those that start later than 30 days after last sorafenib treatment.

The investigator should document the AE start date and additionally tick if an AE was ongoing from previous study or not. The assignment if an AE is ongoing or new will be primarily based on the AE start date and will be done according to the following rules:

- Any AE documented on or after enrolment date in STEP will be considered as new.
- Any AE with start date before STEP enrolment date will be considered as ongoing.
- In case the AE start is partially missing (i.e. day and/or month are missing), the date will be imputed as specified below.
- If the AE start date is completely missing, the answer to the question 'Ongoing from previous study' will be used – 'yes' indicates the AE is ongoing, 'No' indicates the AE is new.

The following imputation will be used for partially missing AE start date, whenever it is necessary to assign the AE to the 'ongoing' or 'new' category:

- If only the day is missing, the first of the month will be used, except if the start month/year are equal to enrolment month/year, then the start day of enrolment will be used.
- If day and month are missing, then 1st of July will be used, except if the start year is equal to the enrolment year, then the start day/month of enrolment will be used.

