## 6.4 Safety

Descriptive statistics will be calculated for the treatment duration. Duration of study treatment within STEP will be calculated in days as the date of the last dose of any study treatment – date of the first dose of any study treatment + 1. Duration in months will be presented in months, calculated by dividing days by 30.4. In addition to the descriptive statistics referenced in section 4.1, the sum of all treatment durations will also be calculated.

Adverse Events (AEs) will be coded according to the most recent version of the Medical Dictionary for Regulatory Activities (MedDRA). AE grading will be documented using version 3.0 of the National Cancer Institute (NCI) Common Terminology Criteria for Adverse Events (CTCAE).

In STEP, AEs ongoing from previous study as well as new AEs occurring during STEP were collected. AEs will be classified as ‘ongoing AE’, ‘new treatment-emergent AE’ or ‘new non treatment-emergent AEs after 30 days after last sorafenib dose’ (see Section 4.5). Tables will be created for ongoing AE, new treatment-emergent AE, and the combination of both. New non treatment-emergent AEs after 30 days after last sorafenib dose will only be listed.

AEs will be summarized by counts and incidence proportions, and grouped by MedDRA system organ class, MedDRA preferred term, and worst CTCAE grade, for the following:

- New TEAEs in STEP:
  - TEAE
  - Drug-related TEAE
  - TEAE leading to dose reduction
  - Drug-related TEAE leading to dose reduction
  - TEAE leading to dose interruption
  - Drug-related TEAE leading to dose interruption
  - TEAE leading to drug discontinuation
  - Drug-related TEAE leading to drug discontinuation
  - TESAE
  - Drug-related TESAE
  - TEAEs leading to death
  - Drug-related TEAEs leading to death
- Ongoing AEs from feeder studies:

- AEs
- Drug-related AEs
- SAEs
- Drug-related SAEs
- All AEs in STEP (ongoing AEs from feeder studies + new TEAEs in STEP)
  - AEs
  - Drug-related AEs
  - SAEs
  - Drug-related SAEs

The numbers of deaths and the primary cause of death (as reported by the investigator) will be tabulated and listed.

Hematology and blood chemistry values will be summarized according to their worst CTCAE grade, where applicable. Hematology and blood chemistry values will be graded based on the applicable laboratory threshold values outlined in NCI CTCAE version 3.0.

Individual time courses of ECOG performance status will be displayed graphically.

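### Does SAP 4.1 need a rule for TACE, given that four patients from a TACE trial are tabulated as sorafenib monotherapy?

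*SAP*

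**What the plan says.** SAP 4.1 sets the column structure: "Tables will be created by treatment group (sorafenib monotherapy, sorafenib+erlotinib". It adds that safety data are not pooled across the two groups and that the single erlotinib patient is only listed. TACE appears nowhere in the SAP.

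The protocol treats TACE in two ways. Sections 4.2.1 and 4.5.2.3 and the Amendment 8 rationale in 10.6.4 call sorafenib with TACE a combination. Sections 4.1 and 4.5.5, which list the treatments patients continue in STEP, name only sorafenib alone or with capecitabine. TACE enters 4.2.2 and 4.5.8 as an exception to the chemotherapy bans, and the flow chart in 11.1 tracks dispensing of sorafenib and capecitabine only.

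SAP Table 1–1 ("Patient numbers of study 12311 by feeder trial") lists 4 patients from 12918. Protocol 10.4.2 identifies 12918 as SPACE, and 10.2.1 describes it: "The SPACE study, a randomized, double-blind study of sorafenib vs placebo in patients with hepatic cellular carcinoma who are receiving TACE treatment".

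On adverse events, SAP 6.4 says "Tables will be created for ongoing AE, new treatment-emergent AE, and the combination of both". SAP 4.5 explains why ongoing events are kept apart and not called treatment-emergent: "Since the STEP data are not combined with data from the feeder trials", the feeder treatment dates are not available.

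**The concern.** The SAP separates one erlotinib patient and refuses to pool safety data across groups, yet has no rule for another combination that the protocol names. The safety objective covers combination treatment as well as sorafenib alone, so a reader may expect TACE patients to be identifiable. Two situations seem to be left open.

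- **TACE during STEP.** A patient who had it would sit in the monotherapy column with nothing to show it. The history suggests the question was live: the sponsor "issued an administrative letter on 11 Dec 2013 to clarify that since the implementation of Amendment 2, concomitant TACE and sorafenib is permissible", and Amendment 4 added dose guidance for TACE. The same amendment dropped erlotinib for want of patients: "All references to erlotinib were removed since none of the subjects that transferred into this study were assigned to erlotinib+sorafenib".
- **Events carried in from 12918.** These began in a trial where TACE was background therapy, but would be counted under monotherapy in the ongoing-event and combined tables. This would apply even if nobody had TACE in STEP.

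At stake is whether the monotherapy column describes what it claims to describe.

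**Working it through.** **1. Inputs.** SAP Table 1–1: 26 feeder trials, 4 patients from 12918, 7 from 12917, none from 12444, total 206. SAP 4.1: one patient on sorafenib+erlotinib.

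**2. The plan's own figures.** The 26 rows sum to 206, and every row percentage agrees with n/206. For 12918, 4/206 = 1.94%, shown as 1.9.

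**3. Size of the monotherapy column.** Assume that all 206 were dosed, so that the safety set equals the enrolled set. The column then holds 206 − 1 = 205 patients. The footnote to Protocol 4.5.3.1 says the erlotinib patient came from SEARCH, which is 12917, so all four patients from 12918 are among the 205.

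**4. Most they can contribute to a row.** If k of the four have a given event, they add k/205:

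| k | percentage points |
|---|---|
| 0 | 0.00 |
| 1 | 0.49 |
| 2 | 0.98 |
| 3 | 1.46 |
| 4 | 1.95 |

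**5. Effect of taking them out.** Let x be the row count and a the number of the four included in it. The row moves from x/205 to (x − a)/201, a difference of (205a − 4x)/(205 × 201). The extremes are a = 4, x = 4, which gives 804/41,205 = +1.95 points, and a = 0, x = 201, which gives −1.95 points. Even complete removal shifts no percentage by more than 1.95 points in either direction.

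**6. Is there evidence of TACE in STEP?** Protocol 4.5.2.3 says that all patients on the TACE combination are off the study. Section 4.5.2.2 says the same of capecitabine, although Table 1–1 has no patient from 12444, the capecitabine trial. That wording therefore does not show that anyone had TACE. The 2013 letter does not either: Protocol 10.4.1 presents it as correcting an oversight, because 4.5.8 had not been aligned with 4.2.2 after Amendment 2. The number from 12918 with TACE in STEP lies between 0 and 4. The inclusion criterion is not restricted to 12918, so 4 is not a proven ceiling for the whole study, but the documents point to no other source.

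**7. Is 12918 special for ongoing events?** Six of the seven patients from 12917, a trial of sorafenib with erlotinib, are also in the monotherapy column (7 − 1 = 6; 6/205 = 2.93%). Protocol 4.2.1 further admits patients who once had sorafenib with other chemotherapy and continued on sorafenib alone. Labelling by STEP treatment, whatever the feeder regimen, is one consistent rule. A footnote for 12918 alone would break it.

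**The case for a change.** The best argument for a change is consistency. A plan that separates a single erlotinib patient should say what it does with another combination the protocol names, particularly when Amendment 2 was written so that SPACE patients could enter STEP and keep having TACE. That nobody remained on TACE at Amendment 8 is no answer, because the final analysis covers all 206 patients. The by-feeder enrolment table gives a trial number without saying that it was a TACE trial. A footnote would be cheap, since the case report form already holds the feeder number: the demography entry in Protocol 11.1 "Includes originating study number, patient number and date of first sorafenib dose in originating study".

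Much of this stands. The SAP is silent, the four patients are unlabelled in the tables, and a note would cost little. But the argument shows that a sentence could be written, not that any table would be wrong without it. The proposed wording records the grouping that SAP 4.1 already produces. TACE use during STEP is harder to establish, because Protocol 4.6.2 requires concomitant medications only in source documents. Without source queries, a statement on it might say no more than that the status is unknown.

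**Conclusion.** No change is needed. This is missing detail that the analyst fills in only one way. Grouping by study drug matches the treatment lists in Protocol 4.1 and 4.5.5 and leaves no patient without a column. Ongoing events are already presented apart from new ones, under a heading that says they come from feeder studies. The combined table is announced as a combination.

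The four patients from 12918 can account for at most 4/205 = 1.95 percentage points of any monotherapy row, if all 206 were dosed. The actual figure may be zero, since the documents show neither TACE during STEP nor an ongoing event in any of the four. The report is descriptive, with no test or threshold that a shift of this size could affect.

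If the SAP is reopened for other reasons, the team may choose to state that patients with concomitant TACE are tabulated by study drug and to flag known TACE use in the listings. That is a labelling preference.
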